In this study, predictive model will be constructed using the EVT database from Zhejiang Provincial People's Hospital as a training cohort, and prospective data from other centers will be used to validate the performance of predictive model. We will randomly select 70% of the patients from the Stroke Center EVT database at Zhejiang Provincial People's Hospital as the training cohort, while the remaining 30% will constitute the internal validation cohort. Within the training cohort, our aim will be to analyze imaging and clinical parameters when constructing the predictive model.

Given the requirement of at least 10 events per candidate variable for model establishment, a minimum of 200 MBE patients is necessary in the training cohort to ensure stable model estimation. Based on a study design with a sample ratio of 7:3 for the training and internal validation sets, at least 290 MBE patients will be required in this study at Zhejiang Provincial People's Hospital. The external validation set will require 100-200 positive samples; considering an approximate 20% incidence rate of MBE in anterior circulation EVT patients, this study will need to include at least 1950 EVT patients.

Statistical analysis

Compare baseline clinical and imaging data of EVT patients with and without MBE across the training, internal validation, and external validation sets. Continuous variables conforming to a normal distribution will be described using means and standard deviations, while those not conforming will be described using medians and quartiles. Categorical variables will be expressed as percentages.

In the training set, factors influencing MBE will be analyzed. Continuous variables will be analyzed using Student's *t*-test or Mann-Whitney U test, while categorical variables will be analyzed using chi-square test and Fisher's exact test. Collinearity among variables will be assessed using Variance Inflation Factors (VIFs), where VIF <10 and Tolerance >0.1 indicate no significant collinearity. Variables with a significance level of *P* <0.1 in univariate analysis will be incorporated into logistic regression analysis using forward stepwise selection method, and odds ratios (ORs) and 95% confidence intervals (CIs) will be calculated. Factors with *P* < 0.05 will be included as independent predictors of MBE in the model. After constructing the predictive model, it will be converted into a dynamic nomogram and deployed on a webpage, generating a dynamic nomogram URL.

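### The total of 1,950 patients covers only the lower end of the 100-200 external MBE events, and the event counts called minima are planned at or near their expected values, with no margin

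*Protocol*

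**What the plan says.** The Sample size section of the protocol builds its total in four steps.

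- **Training.** It starts from a rule of thumb, "Given the requirement of at least 10 events per candidate variable for model establishment", and concludes that "a minimum of 200 MBE patients is necessary in the training cohort to ensure stable model estimation".
- **Lead centre.** It scales up for the split, "Based on a study design with a sample ratio of 7:3 for the training and internal validation sets", and states that "at least 290 MBE patients will be required in this study at Zhejiang Provincial People's Hospital".
- **External validation.** It then says "The external validation set will require 100-200 positive samples; considering an approximate 20% incidence rate of MBE in anterior circulation EVT patients".
- **Total.** It concludes that "this study will need to include at least 1950 EVT patients".

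The split itself is described as a random draw of patients: "We will randomly select 70% of the patients from the Stroke Center EVT database at Zhejiang Provincial People's Hospital as the training cohort". Stratification on MBE status is not mentioned. The section makes no allowance for chance variation in event counts or for an incidence below 20%, and gives no rule that recruitment continues until the counts are reached. The Study population section gives only an expected calendar end, June 2027.

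**The concern.** There are two difficulties, and a smaller third.

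First, the external requirement is a range, but the total is a single number that matches only the bottom of that range. The text does not say so, and a reader could credit the design with up to 200 external events.

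Second, the event counts are worded as requirements, yet the sample size is the number of patients at which those counts are expected on average. A minimum set at its own expected value is missed by chance nearly half the time.

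Third, the 70% draw ignores MBE status, so the number of training events varies even when the lead-centre total is exactly as planned.

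The training count is the protocol's own criterion for stable model estimation. The external count governs the precision of the AUC, the calibration assessment and the decision curves that the Statistical analysis section relies on.

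**Working it through.** **Inputs, all from the Sample size section:** at least 10 events per candidate variable; 200 training events; 7:3 split; 290 lead-centre events; 100-200 external events; incidence about 20%; total at least 1,950. The number of candidate variables is not stated; 200/10 implies 20.

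**Reproducing the plan's figures**

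- Lead-centre events: 200/0.7 = 285.7, so 286; the stated 290 is this figure rounded up. In the other direction, 0.7 × 290 = 203.
- Total with 100 external events: (290 + 100)/0.20 = 390/0.20 = 1,950. This matches exactly.
- Total with 150 external events: 440/0.20 = 2,200. With 200: 490/0.20 = 2,450, which is 500 more than stated.

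**Expected counts.** The protocol does not divide 1,950 between centres. The division implied by its own figures is 290/0.20 = 1,450 at the lead centre (1,015 training, 435 internal validation) and 100/0.20 = 500 external. Expected events at 20% are 0.20 × 1,015 = 203, 0.20 × 1,450 = 290 and 0.20 × 500 = 100.

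**Chance of missing each count** (independent patients, exactly 20% incidence)

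| Count | Distribution | P(below it) |
|---|---|---|
| Training, 200 | Binomial(1015, 0.20) | 0.395 |
| Lead centre, 290 | Binomial(1450, 0.20) | 0.490 |
| External, 100 | Binomial(500, 0.20) | 0.482 |

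**Joint attainment**

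- Training and external: (1 − 0.395) × (1 − 0.482) = 0.605 × 0.518 = 0.31.
- All three: P(training ≥200 and lead centre ≥290), summed over the training count, is 0.459; 0.459 × 0.518 = 0.238. A simulation of 400,000 draws also gave 0.238.
- The probability of 200 or more events among 500 external patients is essentially zero.

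**Sensitivity to incidence** (same 1,450/500 division)

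| Incidence | Training and external met | All three met |
|---|---|---|
| 18% | 0.012 | 0.003 |
| 19% | 0.089 | 0.045 |
| 20% | 0.31 | 0.24 |
| 21% | 0.62 | 0.57 |
| 22% | 0.84 | 0.83 |

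**Size of the shortfalls at 20%.** The 5th percentile is 182 training events, or 182/20 = 9.1 per variable for the implied 20 candidates, and 85 external events. At an assumed AUC of 0.80 (Hanley-McNeil), the 95% half-width is 0.055 with 100 events among 500 patients, 0.059 with 85 among 500, and 0.039 with 200 among 1,000.

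**The split on its own.** Fix exactly 290 events among 1,450 patients and draw 1,015 at random. Training events are then hypergeometric with mean 203 and 5th-95th percentile 191-214, and P(<200) = 0.307.

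**How much of the joint shortfall is due to the split.** With a split stratified on MBE, 290 lead-centre events guarantee 203 in training, so the joint probability of all three minima is 0.510 × 0.518 = 0.264, against 0.238 unstratified. The split therefore accounts for under 3 percentage points; the rest comes from setting the total at expected counts.

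**The case against.** The best defence is that nothing is miscalculated. The total is worded as a floor, it is built from floors on events, and it reproduces exactly. This stands. A reader might infer that the protocol promises 200 external events from 1,950 patients; it does not say so, and 100 lies within its stated range. What is missing is a statement of which end of the range the total corresponds to.

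A second tempting reading is that the unstratified split causes the minima to be met together only one time in four. The documents do not support this. Stratifying moves the joint probability only from 0.238 to 0.264. Moreover, one in four counts 290 as a separate requirement although it is derived from 200; on the two substantive minima the figure is 0.31.

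Third, a shortfall is not a failure of the study. At 20% incidence, training events reach at least 180 with probability 97%, and falling from 100 to 85 external events widens the AUC interval only slightly. This also stands, and it limits the seriousness of the point.

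Fourth, a random draw does not exclude stratification, and its details may be left to an SAP that is not shown. That is fair as to method. However, the protocol itself sets a 200-event minimum beside a draw that, as described, misses it in 31% of splits even when the 290 target is met exactly.

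Finally, recruitment could go beyond 1,950. It could, and that would reduce the shortfall, but the protocol gives no event-based completion rule.

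**Conclusion.** The point holds as one of clarity and missing margin, not as an arithmetic error. The figure of 1,950 is correct for 100 external events and only for that; 200 would need 2,450. The counts of 200, 290 and 100 are planned at or near expectation, so at exactly 20% incidence the training and external minima are both met with probability about 0.31, and all three with probability 0.24.

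These probabilities rest on the implied 1,450/500 division and on independent patients, and they change sharply with an incidence that the protocol itself calls approximate. No single probability should be quoted without that range. The main cause is setting the total at expected counts. The 31% chance that a simple random split falls below 200 training events, given exactly 290, is a separate and smaller matter.

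**What to change.** 1. State in the Sample size section that 1,950 patients give an expected 100 external MBE events, the lower end of the 100-200 range. Describe 203 (training), 290 (lead centre) and 100 (external) as expected counts at 20% incidence, not as guaranteed minima.
2. If the 70/30 split is kept, stratify the random draw on MBE status, so that 290 lead-centre events give 203 in training. Note that this removes split variation only and does not cure a shortfall in total events.

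The cost is one reworded paragraph and one option in the split code. No extra patients are needed. The price is that the stated event counts read slightly less favourably.

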We will record the demographic data (gender, age, hypertension, diabetes, history of atrial fibrillation), site of occlusion, baseline systolic and diastolic blood pressure, prior IVT administration, baseline NIHSS score, NIHSS score at discharge, modified Rankin Score (mRS) at discharge, and TOAST stroke etiology (Trial of ORG 10172 in Acute Stroke Treatment) of each participant. Hematological laboratory results will include baseline glucose, baseline white blood cell count, baseline neutrophil count, baseline hemoglobin, and platelet count. The EVT operator will record the time from stroke onset to puncture (OTP), time from puncture to recanalization (PTR), and degree of blood flow restoration. The occluded vessel will be determined based on intraoperative angiography results, and reperfusion level will be graded using the modified Thrombolysis in Cerebral Infarction (mTICI) score, with complete reperfusion defined as mTICI 2b-3. Clinical assessments will be conducted by neurologists unaware of the clinical diagnosis.

Study groups

- training set

To determine potential predictive factors, imaging and clinical parameters will be enrolled into LASSO regression analysis, which effectively eliminated several irrelevant or multicollinearity independent variables to reduce high-dimensional data. The multivariable logistic regression analysis will be applied to determine the

variables predicting MBE, and the results will be used to create a predictive model based on the training set.

- validation set

The predictive model will be further validated in the validation set.

Outcome assessment

Primary Outcome Measures:

The occurrence of MBE: Patients developed MBE within 3 days post-EVT

Secondary Outcome Measures:

1. The follow-up mRS scores of enrolled patients at 90 days since stroke onset.
2. Evidence of parenchymal hemorrhage (PH type) on cranial imaging during hospitalization.

Sample size

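### Odds ratios and 95% CIs are computed on the same training data that select the predictors, so weak predictors and null ones kept by chance look stronger than they are and their intervals undercover

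*Protocol*

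**What the plan says.** The Statistical analysis section of the protocol fixes the sequence. The data set is named first: "In the training set, factors influencing MBE will be analyzed". Variables with univariate P < 0.1 "will be incorporated into logistic regression analysis using forward stepwise selection method", and then "odds ratios (ORs) and 95% confidence intervals (CIs) will be calculated". The last filter is a threshold of 0.05 on the P value, and whatever passes it "will be included as independent predictors of MBE in the model". The fitted model is then turned into a web-based nomogram.

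The Study groups section adds another data-driven step on the training set: "imaging and clinical parameters will be enrolled into LASSO regression analysis", before the multivariable logistic model.

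The Sample size section asks for "at least 10 events per candidate variable for model establishment" and concludes that "a minimum of 200 MBE patients is necessary in the training cohort".

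Validation, at the end of the Statistical analysis section, uses the AUC, calibration plots, the Hosmer-Lemeshow test and decision curves. The protocol states no selection-adjusted interval, shrinkage or bootstrap of the selection for the ORs.

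**The concern.** An ordinary 95% CI has its stated coverage when the model is fixed before the data are seen. Here a variable reaches the results table only if its estimate in these patients was large enough to pass several significance filters. Three things follow.

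- If the P < 0.05 rule and the interval both rest on the Wald statistic, every retained variable has a CI that excludes 1. A null variable kept by chance therefore has an interval that misses the truth every time.
- A weak predictor survives mainly in samples where it was overestimated, so its reported OR is biased away from 1.
- Calling the survivors independent predictors is an inferential claim about single variables, and these intervals are its only stated support.

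At stake are which factors the publication names as independent predictors of MBE, and the nomogram weights of the weaker ones.

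**Working it through.** **The plan's own figures.** 10 events × 20 candidates = 200 training events. 200 / 0.7 = 285.7, stated as 290. (290 + 100) / 0.20 = 1950, as stated. These reproduce, and they imply 20 candidates and 200 / 0.20 = 1000 training patients. The protocol gives no coverage figure for the ORs.

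**Hand check.** For a standardised predictor, SE(log OR) ≈ 1/√(n·p·q) = 1/√(1000 × 0.2 × 0.8) = 0.079. To reach P < 0.05 the estimated OR must exceed exp(1.96 × 0.079) ≈ 1.17. A true OR of 1.1 that is retained in the right direction is therefore always overestimated. Conditioning on |z| > 1.96, it is retained 22.6% of the time, with 88.7% coverage and a median reported OR of 1.21.

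**Simulation.**
- Inputs from the protocol: n = 1000, 20% event rate, 20 candidates, univariate P < 0.1, forward stepwise, P < 0.05 retention, nominal 95% CI.
- Assumptions, not in the protocol: standard-normal candidates; true ORs per SD of 2.0 (one), 1.5 (two), 1.3 (two), 1.2 (two), 1.1 (three) and 1.0 (ten); pairwise correlation 0 or 0.3; stepwise entry at 0.05; Wald intervals; no LASSO step. There were 1500 replicates per correlation.

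Each cell gives correlation 0 / 0.3:

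| True OR per SD | Probability retained | Coverage if retained | Median reported OR |
|---|---|---|---|
| 1.0 | 4.2% / 5.8% | 0% / 0% | 1.18 / 1.27 |
| 1.1 | 17.4% / 19.7% | 84.6% / 74.4% | 1.24 / 1.31 |
| 1.2 | 53.0% / 47.2% | 95.7% / 90.5% | 1.27 / 1.33 |
| 1.3 | 83.9% / 73.8% | 96.5% / 92.6% | 1.32 / 1.39 |
| 1.5 | 99.7% / 97.6% | 95.4% / 94.6% | 1.50 / 1.55 |
| 2.0 | 100% / 100% | 95.1% / 93.3% | 2.01 / 2.10 |
| All retained | – | 88.9% / 83.1% | – |

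The 20-variable model fitted to the same data without selection covers 93.7% to 95.2% at every OR. The shortfall therefore comes from the selection route and not from the sample size.

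**Second simulation.** A separate run with 200 events, 20 candidates, assumed effects and no LASSO step gave about 84–89% overall, 0% for retained nulls, about 68–86% at OR 1.1 and about 91–98% at OR 1.3 or more.

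**False predictors.** From the table, treating the ten nulls as independent, the chance that at least one is retained is 1 − (1 − 0.042)^10 = 35% at correlation 0 and 1 − (1 − 0.058)^10 = 45% at 0.3. The second simulation counted 37–41% directly.

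**The case against.** **The aim is prediction.** The study sets out to design and validate a predictive model. Performance is judged by AUC, calibration and decision curves in held-out and external patients, and none of these uses the OR intervals. This stands: a reader might infer that external validation is compromised, and the documents do not support that. Exaggerated weights could also show up in the planned calibration plots. However, those measures assess overall predictions and do not re-estimate or correct individual ORs.

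**Strong predictors are hardly affected.** A reader might infer that all the reported intervals fall far below 95%. They do not: at an OR of 1.3 or more per SD, coverage is near nominal, and bias at 1.5 and 2.0 is small.

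**The sizes rest on assumptions.** The protocol gives no effect sizes, correlations or stepwise entry level. Overall coverage and the chance of a false predictor both move with the assumed share of nulls. With 26 candidates, 14 of them null, another simulation found at least one null retained in 58–63% of runs. The Background section lists many factors already linked to MBE, and nothing shows that the rest are null, so no single figure can be claimed.

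**The target matters.** With correlated predictors, a reduced model estimates a different conditional OR from the full model, so part of the drop from 88.9% to 83.1% reflects how truth was defined. The results at correlation 0 do not depend on this, and the problem is still present there.

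**LASSO was not simulated.** The figures describe the route in the Statistical analysis section only. LASSO is also selection on the training data and does not by itself correct the later intervals.

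**The SAP is not shown.** It may add a correction. But the protocol already states the selection rule, the interval and the label, so this is a stated choice and not a detail left open.

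**Conclusion.** The point holds for weak and null predictors. The protocol selects and estimates on the same patients and states no correction. At 200 training events and under the assumed effects, coverage is about 83–89% over retained variables, 0% for retained nulls and about 70–85% for a true OR of 1.1 per SD, reported at about 1.23–1.31. It is about 91–98% for an OR of 1.3 or more. The zero for retained nulls follows from the Wald retention rule whatever the effects; the other figures are illustrative.

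This should be changed because the protocol makes an inferential claim that its intervals cannot carry for the weaker variables. It does not invalidate the model, its discrimination or its external validation.

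**What to change.** 1. Report ORs and 95% CIs from a pre-specified model with no outcome-driven selection. Limit it to predictors known by the end of EVT, which excludes the NIHSS and mRS at discharge listed under Clinical assessments. Limit it also to about 20 parameters at 200 events, to keep to the protocol's own rule of 10 per candidate. The Radiological and Clinical assessments sections list about 26 variables even without the discharge scores (200 / 26 = 7.7 events each), so the list has to be cut on prior knowledge before the outcome is examined.
2. State one selection procedure, reconciling the LASSO route with the univariate and stepwise route. Bootstrap it in full and report how often each final-model variable is selected.
3. Present the final-model coefficients as prediction weights, and do not call selected variables independent predictors on the strength of post-selection P values.

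The cost is a change of wording, the bootstrap and one extra table. Intervals will be wider and some P values less favourable. No patient procedure or data collection changes.

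### The nomogram is built from unshrunken logistic coefficients fitted to the data that chose the predictors, so its predicted risks are expected, on average, to be somewhat too extreme in new patients

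*Protocol*

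**What the plan says.** The model-building path is described twice.

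- **Study groups, training set.** "imaging and clinical parameters will be enrolled into LASSO regression analysis", which here serves to eliminate variables. A multivariable logistic regression follows, and "the results will be used to create a predictive model based on the training set".
- **Statistical analysis.** "In the training set, factors influencing MBE will be analyzed". Variables passing a univariate screen at P < 0.1 "will be incorporated into logistic regression analysis using forward stepwise selection method", with odds ratios and 95% confidence intervals. Those with P < 0.05 "will be included as independent predictors of MBE in the model". Once the model exists, "it will be converted into a dynamic nomogram and deployed on a webpage".

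Neither account mentions penalised final coefficients, a shrinkage factor, an optimism correction or recalibration. The rest of the Statistical analysis section assesses calibration by plots and the Hosmer-Lemeshow test, and clinical usefulness by decision curves. It does not say that the nomogram will be adjusted in the light of the results.

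**The concern.** When the same data choose the predictors and estimate their coefficients, the chosen coefficients tend to be too large. In new patients, high predicted risks then tend to be too high and low ones too low, which shows as a calibration slope below 1. The LASSO step does not prevent this as written: it shrinks coefficients while selecting, but the later logistic regression estimates them afresh and loses the shrinkage. Choosing between the two routes therefore does not settle the matter.

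The product is an individual probability, and the Background says its purpose is to support triage and early intervention. Calibration and net benefit at risk thresholds, which the plan uses to judge the model, both depend on absolute risk and not only on ranking. Part of any miscalibration found at the other centres would then come from the way the model was estimated.

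**Working it through.** **Inputs from the Sample size section.** 10 events per candidate variable, 200 training events, a 7:3 split, about 20% MBE incidence, and 100 to 200 external events.

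**The plan's own figures reproduce.**
- 200 / 10 = 20 candidate variables.
- 200 / 0.7 = 285.7, stated as 290.
- (290 + 100) / 0.20 = 1950.
- 200 / 0.20 = 1,000 training patients.

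**Input the protocol does not give.** Model strength. It is an assumption below and is varied.

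**Step 1: heuristic shrinkage.** For a model with all p candidates, S = 1 − p/LR, where LR = −n ln(1 − R²cs). At 20% incidence the maximum R²cs is 1 − (0.2^0.2 × 0.8^0.8)² = 0.632, and R²cs = Nagelkerke R² × 0.632. With p = 20 and n = 1,000:

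| Assumed Nagelkerke R² | LR | S | Events needed for S = 0.9 |
|---|---|---|---|
| 0.15 | 99.7 | 0.80 | 360 |
| 0.20 | 135.2 | 0.85 | 265 |
| 0.30 | 210.4 | 0.91 | 169 |
| 0.40 | 291.6 | 0.93 | 122 |

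So 200 events for 20 candidates do not by themselves make shrinkage unnecessary unless the model is fairly strong.

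**Step 2: simulation of both routes.** Each run had 1,000 training patients, about 200 events and 20 candidates. Six candidates had real effects (log odds ratios per SD of 0.6, 0.5, 0.4, 0.3, 0.2 and 0.15, multiplied by 0.6, 1 or 1.5). The slope was measured in 30,000 to 40,000 new patients from the same population. The stepwise route used 150 runs per scenario, with predictors independent or correlated (0.4 between neighbours). The LASSO route used 40 runs per scenario with independent predictors, five-fold cross-validation, a logistic refit, and a second refit of terms with P < 0.05.

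| Assumed true AUC | Stepwise: mean slope | Share of models with slope < 1 | LASSO then refit: mean slope | Share with slope < 1 | LASSO coefficients kept: mean slope |
|---|---|---|---|---|---|
| 0.66 | 0.837–0.857 | 87% | 0.861 | 80% | 1.139 |
| 0.74–0.75 | 0.912–0.947 | 71–86% | 0.896 | 82.5% | 1.072 |
| 0.81–0.82 | 0.947–0.950 | 74–78% | 0.945 | 72.5% | 1.105 |

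With ten equally weak predictors (log odds ratio 0.2 each, true AUC 0.67), the stepwise mean slope was 0.75 and 99% of models had a slope below 1.

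**Step 3: sensitivity to the assumptions.** Other stepwise runs at true AUC 0.78 to 0.89, with 20 to 26 candidates, gave mean slopes of 0.90 to 0.96, with 12% to 28% of models at slope 1 or above. Runs with 26 candidates, 12 of them with real effects, and 1,015 patients gave 0.66, 0.81 and 0.90 at true AUC 0.64, 0.70 and 0.75. Direction is stable across all of these; size is not.

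**Step 4: what the slope means for one patient.** Assume that a predicted 20% is correct on average. Then true logit = logit(0.20) + slope × [logit(predicted) − logit(0.20)], with logit(0.20) = −1.386 and logit(0.70) = 0.847.
- Slope 0.84: −1.386 + 0.84 × 2.234 = 0.490, a risk of 62%.
- Slope 0.95: −1.386 + 0.95 × 2.234 = 0.736, a risk of 68%.

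**Step 5: does a correction work?** A bootstrap shrinkage factor covering the whole selection process moved the mean slope to between 1.00 and 1.06 in four scenarios. The mean distance of the slope from 1 fell in two of them and did not change materially in the other two.

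**The case against.** **The statistical analysis plan is not shown and may add shrinkage.** The protocol never uses the words unpenalised or maximum likelihood; that reading is inferred from ordinary logistic regression reported with odds ratios and confidence intervals. This stands as a caveat. It does not remove the point, because the protocol states the whole sequence: thresholds, selection method, retention rule and conversion to a nomogram. What is criticised is that stated sequence.

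**A reader might infer that the risks will certainly be too extreme.** The documents and the simulations do not support that. In the main stepwise runs, 13% to 29% of models had a slope of 1 or more (1% with uniformly weak predictors). With strong predictors the average shortfall is only about 5%. The Background names several predictors it regards as reliable, so a strong model is plausible.

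**A reader might infer that patients would be triaged on uncorrected risks.** The study is an observational registry, and nothing in the protocol directs care from the score during it. A 30% internal validation set and the external centres, with calibration plots, would probably reveal the problem, and the model could be recalibrated afterwards. That limits the consequence. What remains is that no correction is planned.

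**A reader might infer that LASSO coefficients should be the default.** They over-shrink on average (mean slope 1.06 to 1.14). In runs with five or six real predictors, the mean distance of the slope from 1 was 0.10 both for stepwise and for retained LASSO at AUC 0.81. At AUC 0.845 it was 0.07 for stepwise against 0.11 for retained LASSO. This objection stands, and the remedy takes account of it.

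**Conclusion.** The point holds as an expectation. On either route the protocol estimates the final coefficients on the data that selected them and deploys the model without shrinkage, so predicted MBE risks are expected to be somewhat too extreme in new patients, on average and not in every sample. At 200 training events the mean calibration slope is roughly 0.84 to 0.95, and lower if the predictors are weak.

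The size rests on assumed model strength, on linear candidate terms, and on new patients resembling the training population. Differences in case mix at other centres could move the slope either way. The correction is cheap and worth making before the model is built.

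**What to change.** In Statistical analysis, between the selection of predictors and the construction of the nomogram, add a step to this effect: a uniform shrinkage factor will be estimated in the training set by repeating the entire selection and fitting process in bootstrap samples; the coefficients will be multiplied by this factor, the intercept re-estimated, and the nomogram built from the shrunken model. Align the training-set text under Study groups, so that the same step applies whichever selection route is retained. Odds ratios and confidence intervals of the unshrunken model can still be reported.

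Building the nomogram from the cross-validated LASSO coefficients, with no refit and no P < 0.05 filter afterwards, is an acceptable alternative.

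**Cost.** Protocol wording and some R code, which is already planned software; no further patients or data. Downsides are possible mild over-shrinkage (mean slope about 1.00 to 1.06 with the bootstrap factor, 1.06 to 1.14 with retained LASSO) and little gain if a few strong predictors dominate. For LASSO only, conventional odds ratios, confidence intervals and P values are lost.
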